6.2 Specimen Collection and Storage

- **Blood specimens** will be collected by venipuncture or from a venous catheter placed by a trained medical person who will remain at the bedside to monitor the subject continuously.
- For screening, a maximum of 22 mL (4½ tsp) will be drawn to measure hormones if not performed previously, a complete blood count and a chemistry panel, and 24 mL (5 tsp) will be drawn during the screening OGTT. During the study, we will draw 64 mL (12¾ tsp) during each HCG-ST (Visits 1-4 and 8-11), 330 mL (66 tsp) during each CCT (Visits 4 and 11), and 272 mL (54 tsp) during each FS-IVGTT (Visits 5 and 12). We will also draw an additional 20 mL (4 tsp) to measure salicylate levels (Visits 1, 6, 7 and 8) and fasting lipid profiles, and an additional 5 mL (1 tsp) to measure progesterone for ovulation detection as needed only if warranted by the BBT response.
- **MNC Isolation and Processing:** Blood samples are collected in tubes containing Na-EDTA as an anticoagulant. A 12 ml sample will be layered over 12 ml of polymorphonuclear cell isolation medium (Polymorphprep™, Accurate Chemical and Scientific Corporation, Westbury, NY). Samples will be centrifuged at 450 x g for 30 minutes at 18°C resulting in separation of two bands above the red blood cell pellet. MNC present in the top band will be harvested with a Pasteur pipette and washed repeatedly with Hank's buffered saline solution (HBSS) yielding greater than 95% pure MNC.⁴⁶ A fresh portion of MNC will be reconstituted

in HBSS for ROS generation or suspended in RPMI 1640 medium for culture. A second MNC portion will be suspended in RNAlater reagent (Qiagen, Germantown, MD) for 24 hours at 4°C to stabilize RNA, centrifuged at 6,000 x g for 5 minutes at 4°C to yield a pellet that will be stored at -80°C until processing for real time-PCR (RT-PCR). A third MNC portion will be suspended in phosphate buffered saline (PBS – pH 7.4), centrifuged at 13,000 x g for 2 minutes at 18°C to yield a pellet that will be stored at -80°C until processing for Western blotting. A fourth portion of MNC will be used to prepare nuclear extracts of DNA-binding protein with a method described by Andrews et al., and will subsequently be stored at -80°C until processing for electrophoretic mobility shift assays.⁴⁷

- Plasma and/or serum will be separated from whole blood through centrifugation and aliquoted into 1.5 ml polypropylene microtubes for storage.
- Individual aliquoted MNC, plasma or serum samples will be placed in a box labeled with the study ID and stored in a -80°C freezer.
- Samples will be labeled with a numbering system for identification of the test result. The numbering system will give each subject a unique identifier, and indicate which study visit each sample is from designated as V1, V2, V3, etc. immediately after the subject number.
- Remaining samples will be stored indefinitely future study as needed.

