6.1 Subject-Related Procedures

- *Screening* of volunteers to confirm the diagnosis of PCOS will typically be based on previously measured hormone levels. It is anticipated that most subjects with PCOS will be diagnosed by the PI just prior to study entry, and will likely involve performance of a hormonal evaluation within 6 months of beginning the study. However, the timing of previous hormone measurements used to diagnose PCOS will be left to the discretion of the PI. If the relevant tests for this purpose have not been performed previously, the necessary hormone levels will be obtained from a screening blood draw which will also be used to measure a CBC and CMP (maximum 22 ml). Assays to measure prolactin, TSH, LH, FSH, total testosterone, free testosterone, androstenedione, DHEA-S and 17-hydroxyprogesterone (17OHP) along with the CBC and CMP will be performed by the UI Health Clinical Pathology Laboratory. Pregnancy will be ruled out in all subjects immediately prior to study testing before and after treatment with salsalate or placebo using a urine test sensitive enough to detect >50 mIU/L of HCG.
- *Screening* of volunteers with an OGTT to rule out diabetes and to determine IR status will be performed in the CCTS CRC prior to study entry after an overnight fast of ~12 hours. A polyethylene intravenous catheter will be inserted in an arm vein for blood sampling at ~9:00 AM. The size of the catheter (i.e. 18-23-gauge) will be of suitable caliber for the size of the vein used to gain access. A baseline blood sample (9 ml) will be drawn in the fasting state. A 75 gram glucose beverage will subsequently be ingested over 10 minutes. Blood samples (9 ml each) will again be drawn at 30, 60, 90, 120 and 180 minutes following glucose ingestion. Every attempt will be made to insert the intravenous catheter and obtain blood samples on time. However, a sample may be obtained within a fifteen minute window after the scheduled time due to any unforeseen technical difficulty. Upon completion of the test, the indwelling catheter will be removed and subjects will be fed a high carbohydrate snack. Blood glucose and plasma insulin levels will be measured by the UI Health Clinical Pathology Laboratory.

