7.0 Expected Risks/Benefits

Risks

- **Venipuncture / Venous Catheter Blood Sampling** – For screening, we will draw a maximum of 22 mL (4½ tsp) to measure hormones if not performed previously, a complete blood count and a chemistry panel, and 24 mL (5 tsp) during the screening OGTT. During the study, we will draw 64 mL (12¾ tsp) during each HCG-ST, 330 mL (66 tsp) during each CCT, and 272 mL (54 tsp) during each FS-IVGTT. We will also draw an additional 20 mL (4 tsp) to measure salicylate levels and fasting lipid profiles, and an additional 5 mL (1 tsp) to measure progesterone for ovulation detection only if warranted by the BBT response.

The *Study Visit Blood Sampling Plan* included as an Appendix provides a detailed accounting of the volume of blood that will be drawn from each subject during the entire study. These flow sheets provide a detailed breakdown of the tubes that will be used, the volumes that will be drawn, and the types of measurements that will be performed. The *Laboratory Flow Charts* also included as an Appendix illustrates how the collected blood will be utilized for molecular work and cell culture in the PI's laboratory to effectively generate key data to address Aims of the study.

The total amount of blood that will be drawn on each subject during screening and the HCG-ST, CCT and the FS-IVGTT is expected to be <1,500 ml consisting of no more than 750 ml obtained ~12 weeks apart which again is a longer interval than the typical clinical practice standard for blood donations. All subjects will be screened for blood count. The decision to proceed with study participation will be reviewed on a case-by-case basis after taking into consideration the health status of the individual if the pre-study screen reveals a hemoglobin <11.6 grams; or in the case of a subject who weighs <70.8 kg, if the pre-study hemoglobin is <12.6 grams. In the latter case, blood sampling will be limited to 10.5 ml/kg within an 8 week period. If the complete blood count (CBC) performed during initial screening reveals evidence that low hemoglobin is due to iron deficiency anemia in an otherwise eligible volunteer, iron supplementation (ferrous sulphate 325 mg twice daily) will be recommended and a CBC will be performed at appropriate intervals until higher acceptable hemoglobin meeting the above criteria is documented before the volunteer enters the protocol.

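### Minor: the screening OGTT blood volume is stated as 24 mL in Sections 6.2 and 7.0, but the draws in Section 6.1 add up to 54 ml

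*Combined protocol and SAP*

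**What the plan says.** Section 6.1 sets out the screening OGTT draw by draw. At baseline, "A baseline blood sample (9 ml) will be drawn in the fasting state". After the glucose drink, "Blood samples (9 ml each) will again be drawn at 30, 60, 90, 120 and 180 minutes following glucose ingestion".

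Section 6.2 gives the total for the same test: "24 mL (5 tsp) will be drawn during the screening OGTT". The risk text in Section 7.0 gives the same total: "24 mL (5 tsp) during the screening OGTT".

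Section 7.0 also sets the rules that this volume counts toward. A low screening hemoglobin triggers case-by-case review, with a separate threshold "in the case of a subject who weighs <70.8 kg, if the pre-study hemoglobin is <12.6 grams". For those women, "blood sampling will be limited to 10.5 ml/kg within an 8 week period". For all participants, blood from screening and the three main tests is expected to stay below 1,500 ml, with "no more than 750 ml obtained ~12 weeks apart". Section 7.0 refers to an appendix, the Study Visit Blood Sampling Plan, which "provides a detailed accounting of the volume of blood that will be drawn from each subject during the entire study". The appendix is listed, but its content is not in the text available to this review.

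**The concern.** The per-draw volumes and the stated total for one test cannot both be right. This does not look like a text-extraction fault: 9 ml appears twice in Section 6.1, 24 mL appears in two separate sections, and the teaspoon conversion agrees with 24.

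The figure matters because it enters a participant safety limit. Screening takes place 1 to 4 weeks before the protocol starts, and Visits 1 to 5 fall in its first week (Section 6.0). The OGTT is therefore at most about 5 weeks before the end of baseline testing, inside the 8-week window. If 9 ml is drawn six times and 24 mL is counted, a woman under the 10.5 ml/kg limit could give 30 ml more than her record shows.

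**Working it through.** **Inputs.** OGTT: one baseline draw plus five later draws, 9 ml each (6.1). HCG-ST: four draws of 16 ml (6.1). CCT: one draw of 90 ml and three of 80 ml (6.1). FS-IVGTT: 34 samples of 8 ml (6.1). Stated totals: 24, 64, 330 and 272 mL (6.2 and 7.0). Screening hormones, blood count and chemistry: at most 22 mL (6.2).

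**Check of each stated total, as draws × volume per draw.**

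| Test | From the draws | Stated | Agrees |
|---|---|---|---|
| HCG-ST | 4 × 16 = 64 | 64 | yes |
| CCT | 90 + 3 × 80 = 330 | 330 | yes |
| FS-IVGTT | 34 × 8 = 272 | 272 | yes |
| OGTT | 6 × 9 = 54 | 24 | no |

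The gap is 54 − 24 = 30 ml. Dropping one draw does not close it (5 × 9 = 45), and 24 is not a multiple of 9. With six draws, 24 mL needs 24 / 6 = 4 ml per draw.

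**First block: screening plus the baseline tests.** The three tests total 64 + 330 + 272 = 666 ml. With the full 22 mL screening draw, and before any Visit 1 salicylate or lipid blood:

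- with 24 mL: 22 + 24 + 666 = 712 ml
- with 54 ml: 22 + 54 + 666 = 742 ml

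**Against the general statements in Section 7.0**, which cover screening and the three tests:

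- room under 750 ml: 750 − 712 = 38 ml, or 750 − 742 = 8 ml
- whole study, adding the second round of tests: 712 + 666 = 1,378 ml, or 742 + 666 = 1,408 ml, both below 1,500 ml

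**Against the 10.5 ml/kg limit.** The 30 ml difference carries straight into the count. As an illustration, at 60 kg the limit is 60 × 10.5 = 630 ml. The planned block must then be cut by 712 − 630 = 82 ml if the OGTT takes 24 mL, or by 742 − 630 = 112 ml if it takes 54 ml. Planning the cut on the wrong figure leaves a 30 ml error.

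**The case against.** The contradiction itself is hard to dispute. The case on the other side concerns its consequences, and much of it stands.

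- **The wrong figure is not identified.** If 24 mL is right, the totals in Sections 6.2 and 7.0 are correct and the only slip is the per-draw volume in Section 6.1. The under-count arises only if 9 ml draws are actually taken. This stands.
- **Staff may not count from the narrative.** Section 7.0 points to an appendix that details tubes and volumes. A miscount in practice is therefore possible but not shown. This stands.
- **Few women are affected.** The limit applies only under 70.8 kg with hemoglobin below 12.6 grams. Anemia is an exclusion, iron deficiency is treated before entry, and low values are reviewed case by case. Below about 63.4 kg (666 / 10.5) the three tests alone exceed the limit, so sampling must be cut there under either figure. This also stands, although the size of the cut still depends on the OGTT volume.

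A reader might infer that 54 ml must be right, because the limit at its own weight threshold is 70.8 × 10.5 = 743.4 ml, close to 742 ml. The documents do not support this. Section 6.0 also requires salicylate and lipid blood at Visit 1, and the margin is only 743.4 − 742 = 1.4 ml. If the Visit 1 share of the additional 20 mL is assumed to be 5 to 20 ml, the block becomes 747 to 762 ml and the match is gone. There is also a clue the other way. The FS-IVGTT uses 8 ml per sample for glucose, insulin, C-peptide and FFA, while the OGTT measures only glucose and insulin, so 4 ml per draw is plausible. Neither clue settles the matter.

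**Conclusion.** The plan is wrong as written on this figure, and the point is minor. The OGTT volume is 54 ml by the draws in Section 6.1 and 24 mL in Sections 6.2 and 7.0, a 30 ml contradiction that no other available text resolves. If 9 ml draws are taken and 24 mL is counted, blood loss is under-counted by 30 ml for the few women under the 10.5 ml/kg limit. The block totals of 712 and 742 ml assume the full 22 mL screening draw and leave out Visit 1 salicylate and lipid blood.

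A reader might infer that the 750 ml statement is breached, since adding Visit 1 salicylate and lipid blood could take the first block past it. The documents do not support that: the statement covers screening and the three tests, and either OGTT figure keeps those under 750 ml and under 1,500 ml. Nor do they show that any participant would in fact be over-drawn. No endpoint, power calculation or analysis is affected.

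**What to change.** Check the Study Visit Blood Sampling Plan for the intended OGTT volume, then make one of two changes:

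- if 9 ml draws are intended, change 24 mL (5 tsp) to 54 mL (about 11 tsp, at the roughly 5 mL per teaspoon used elsewhere in Section 6.2) in Sections 6.2 and 7.0; or
- if 24 mL is intended, change 9 ml to 4 ml per draw, in both places, in Section 6.1.

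Until this is settled, count 54 ml toward the 10.5 ml/kg limit, so that any error is on the side of drawing less. The cost is a text correction only, with no change to design, sample size or analysis.

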6.3 Study Medication Preparation and Dispensing

- A research pharmacist from the Investigational Drug Service (IDS) will prepare the study medication consisting of 500 mg capsules of salsalate along with an identical placebo. The PI currently holds an IND for salsalate administration (IND #113845).
- A research pharmacist will also prepare all of the clamp infusates.
- The study medication, HCG and clamp infusates will all be stored in the IDS and dispensed by an IDS research pharmacist when needed for use in the study.

6.4 Protected Health Information (PHI) and Other Data Collected

- PHI data will be collected at the time of study enrollment
- Subject demographics will be used for descriptive purposes.
- Anthropometric data (height and weight) and body composition data from the DEXA scan and abdominal MRI will also be used for descriptive purposes.
- Diet logs will be collected.

6.5 Data Storage and Management

- All research data will be coded using unique identifiers. Once the subject has been assigned a unique identifier, all data will carry this label. Only the PI will have the original identifier information and this information will be kept in a password-protected spreadsheet on his encrypted and password protected personal computer or secure departmental server in his locked office at UIC located in CMRB 1111.

- All subject visit data will be transcribed from a written data sheet to password protected files on an encrypted university computer and the original data sheet will be kept in a subject binder. Subject binders will be kept in a locked cabinet in the PIs locked office.
- Study personnel and the PI will have access to the study information.
- Information will be kept indefinitely.

6.6 Specimen Analyses – Laboratory Assays

- *ROS Generation Assay:* Respiratory burst activity of MNC (4×10^5 cells/ml) will be measured by detection of superoxide radical via chemiluminescence. A 500 μ l aliquot of MNC (400 cells/ μ l) is added to duplicate cuvettes containing a spin bar. The cuvettes are placed into a two-channel lumi-aggregometer (Chronolog Corporation, Haverton, PA). 15 μ l of 10mM luminol followed by 1 μ l of 10mM formylmethionyl leucinyl phenylalanine are added to each cuvette. Chemiluminescence is recorded in mV by computer software (Chronolog Aggrolink). The gain is adjusted to visualize the curves within range of the displayed graph. The peak responses of the duplicate samples recorded to calculate the mean peak. This method was developed by Thusu and Dandona,⁴⁸ and is similar to that published by Tosi and Hamedani.⁴⁹ In this assay system, superoxide radical release measured by chemiluminescence correlates linearly with that measured by the ferricytochrome C method. There is also a dose-dependent chemiluminescence inhibition by superoxide dismutase and catalase, and diphenylene, a specific inhibitor of NADPH oxidase, the superoxide producing enzyme. The specific inhibitory effect of diphenylene iodonium on NADPH oxidase has been established by Hancock and Jones.⁵⁰ As validated in our laboratory, the variation of ROS generation by MNC in humans using this method varies by less than 8% over a 2 week period.^{12,51}
- *NADPH Oxidase p47^{phox} Subunit, p65 NF κ B Subunit, I κ B, TNF α , IL-6 and IL-1 β Real-Time PCR (RT-PCR):* MNC are suspended in RNAlater reagent (Qiagen, Germantown, MD) for 24 hours at 4°C to stabilize RNA, centrifuged at 6,000 x g for 5 minutes at 4°C to yield a pellet that is stored at -80° C until processing for RT-PCR. Total RNA is isolated from MNC (~20 mg) using an RNAeasy kit (Qiagen, Germantown, MD). The isolated total RNA (1 μ g) is treated with DNase (Life Technologies, Gaithersburg, MD), and reverse-transcribed using TaqMan reverse transcription reagents (PE Biosystems, Foster City, CA) and oligo(dT) primers according to the manufacturer's instruction. Primers and probes for the individual inflammation marker genes are selected using PRIMER EXPRESS software (PE Biosystems, Foster City, CA). The internal probes and a 28S rRNA probe are constructed as previously described.⁵² Internal probes are labeled at the 5'-ends with a reporter dye (6'-carboxyfluorescein), and at the 3'-end with a non-fluorescent quencher; and subsequently phosphate-blocked at the 3'-end to prevent extension. The 5'-end of the 28S rRNA probe is labeled with VIC, a proprietary fluorescent dye (PE Biosystems, Foster City, CA). Each set of target primers and probe are co-amplified with 28S rRNA primers and probe. Fluorescence is measured at each amplification cycle in an ABI Prism 7700 Sequence Detection System (Perkin Elmer/Applied Biosystems, Foster City, CA). The signal for the 28S rRNA is used to normalize against differences in RNA isolation and RNA degradation, and in the efficiencies of the reverse transcription and PCRs. All samples are run in triplicate and quantified by normalizing the inflammation marker mRNA signal with the 28S signal. The final quantification is achieved with a relative standard curve.⁵²

- *NADPH Oxidase p47^{phox} Subunit, p65 NF κ B Subunit and I κ B Western Blotting:* As previously described,⁵³ MNC cell lysates are prepared by adding 1 ml of boiling lysis buffer (1% SDS), 1mM sodium ortho-vanadate, and 10 mM Tris (pH 7.4) to MNC pellets. Total protein concentrations are determined using BCA protein assay (Pierce Chemical Co., Rockville, IL). Total cell lysate (60 mcg) are electrophoresed on 10% gels for p47^{phox} subunit and I κ B. The proteins are transferred to a polyvinylidene diflouride membrane and incubated with a monoclonal antibody against p47^{phox} subunit (Transduction Laboratories Inc., San Diego, CA) or a polyclonal antibody against I κ B (Rockland, Gilbertsville, PA). The membrane is washed and developed using super signal chemiluminescence reagent (Pierce Chemical Co.). Densitometry is performed using Carestream Molecular Imaging software version 5.0.2.30 (Rochester, NY).
- *NF κ B Electrophoretic Mobility Shift Assay (EMSA):* As previously described,^{46,47} DNA-binding protein extracts are prepared from MNC pellets, and total protein concentrations are determined using BCA protein assay (Pierce Chemical Co., Rockville, IL). The NF κ B gel retardation assay is performed using an NF κ B-binding protein detection kit (Life Technologies, Inc. Long Island, NY). The double-stranded oligonucleotide containing a tandem repeat of the consensus sequence for the NF κ B-binding site is radiolabeled with γ -P³² by T4 kinase. The nuclear extract (5 μ g) is mixed with incubation buffer and preincubated at 4°C for 15 minutes. Labeled oligonucleotide (60,000 cpm) is added, and the mixture is incubated at room temperature for 20 minutes. Samples are electrophoresed on a 6% nondenaturing polyacrylamide gel that is dried under vacuum and exposed to x-ray film. Densitometry is performed as described above.
- *MNC Culture:* A blood sample will be drawn at 0 and 120 minutes of the CCT for MNC isolation. Whole blood will be diluted 1:2 with PBS (pH 7.4) and underlayered with histopaque-1077 for density gradient centrifugation (400g for 45 minutes) as previously described.⁵⁴ The pellet is obtained from the last wash and resuspended in RPMI 1640 culture medium (2mM L-glutamine, 100 U/ml penicillin, 100 ug/ml streptomycin, 90 mg/dl glucose) at a final concentration of 5X10⁶ cells/ml. MNC isolated from the pre-CCT fasting blood sample will be cultured in medium supplemented with palmitate bound to fatty acid-free bovine albumin (4%) at varying concentrations spanning the physiological postabsorptive to pathophysiological range (0.4, 0.8, 1.2 and 2.0 mM), in the presence and absence of 1 ng/ml of lipopolysaccharide (LPS) endotoxin (Sigma, St Louis, MO). MNC isolated from the 120 minute CCT blood sample will be cultured without FFA supplementation in the presence and absence of 1 ng/ml of LPS. After a 24 hour incubation (5% CO₂ at 37°C), MNC supernatants will be collected and stored at -80°C until assayed.
- *Plasma Measurements:* All assays will be performed in the Reproductive Endocrine and Inflammation Laboratory except those for salicylate and progesterone which will be measured by the Clinical Chemistry Laboratory at IU Hospital. Glucose concentrations will be measured by the glucose oxidase method (YSI, Yellow Springs, OH) while plasma insulin concentrations will be measured by direct double antibody RIA (Linco Research, St. Charles, MO). C-peptide will be measured by a 2-site immunenzymatic sandwich assay (Roche Diagnostics, Indianapolis, IN). FFA will be measured by an enzymatic colorimetric assay (Wako Diagnostics, Mountain View, CA). TNF α , IL-6 and IL-1 β levels in plasma and in MNC culture supernatants will be measured by ELISA (Quantikine, R&D Systems, Minneapolis, MN). CRP levels will be measured by a high sensitivity ELISA (Alpha Diagnostics International, San Antonio, TX). Levels of LH, androstenedione, testosterone, DHEA-S, 17OH-progesterone and progesterone will be measured in duplicate by RIA (MP

Biomedicals LLC, Solon, OH). Sex Hormone Binding Globulin will be measured by electrochemiluminescence (Mayo Clinic, Rochester, MN). To reduce interassay variability, all samples from an individual subject will be measured in the same assay at the end of the study.

7.0 Expected Risks/Benefits

Risks

- **Venipuncture / Venous Catheter Blood Sampling** – For screening, we will draw a maximum of 22 mL (4½ tsp) to measure hormones if not performed previously, a complete blood count and a chemistry panel, and 24 mL (5 tsp) during the screening OGTT. During the study, we will draw 64 mL (12¾ tsp) during each HCG-ST, 330 mL (66 tsp) during each CCT, and 272 mL (54 tsp) during each FS-IVGTT. We will also draw an additional 20 mL (4 tsp) to measure salicylate levels and fasting lipid profiles, and an additional 5 mL (1 tsp) to measure progesterone for ovulation detection only if warranted by the BBT response.

The *Study Visit Blood Sampling Plan* included as an Appendix provides a detailed accounting of the volume of blood that will be drawn from each subject during the entire study. These flow sheets provide a detailed breakdown of the tubes that will be used, the volumes that will be drawn, and the types of measurements that will be performed. The *Laboratory Flow Charts* also included as an Appendix illustrates how the collected blood will be utilized for molecular work and cell culture in the PI's laboratory to effectively generate key data to address Aims of the study.

The total amount of blood that will be drawn on each subject during screening and the HCG-ST, CCT and the FS-IVGTT is expected to be <1,500 ml consisting of no more than 750 ml obtained ~12 weeks apart which again is a longer interval than the typical clinical practice standard for blood donations. All subjects will be screened for blood count. The decision to proceed with study participation will be reviewed on a case-by-case basis after taking into consideration the health status of the individual if the pre-study screen reveals a hemoglobin <11.6 grams; or in the case of a subject who weighs <70.8 kg, if the pre-study hemoglobin is <12.6 grams. In the latter case, blood sampling will be limited to 10.5 ml/kg within an 8 week period. If the complete blood count (CBC) performed during initial screening reveals evidence that low hemoglobin is due to iron deficiency anemia in an otherwise eligible volunteer, iron supplementation (ferrous sulphate 325 mg twice daily) will be recommended and a CBC will be performed at appropriate intervals until higher acceptable hemoglobin meeting the above criteria is documented before the volunteer enters the protocol.

The risk of developing anemia due to blood draws during the study is uncommon but still possible in subjects with a pre-study hemoglobin at the lower limit of study eligibility (<12.0 grams, or <13.0 grams for weight <70.8 kg). Subjects in this circumstance will be advised to take iron during the study (ferrous sulphate 325 mg twice daily) as a precaution. Additional iron supplementation may be recommended as appropriate if a complete blood count (CBC) performed at the end of the study reveals a low hemoglobin.

The potential risks to the subjects associated with venipuncture needle sticks or IV catheter insertions include discomfort, possible bleeding/hematoma (~1/1000) at the site, rarely an infection, and uncommonly feeling faint from the procedure. These risks will be minimized by allowing only experienced nurses or doctors to insert intravenous lines. From

time to time, difficulty may be encountered in performing venipuncture or inserting an intravenous catheter even after several attempts. In this instance, a subject may be escorted by a physician or a research nurse from the CRC to the Imaging and Diagnostics Services Short Stay Unit located in Suite 2600 on the 2nd floor of UI Heath Hospital at [name] immediately across the skyway adjacent to the CRC, where a member of the IV-PICC Team will perform the venipuncture or insert the intravenous catheter using ultrasound guidance at no additional risk. The subject will subsequently be escorted back to the CRC to complete the particular study visit. Use of the IV-PICC Team may extend the CRC study visit by up to 2 hours.

The studies will be performed on the CCTS CRC, which provides staff that assists the P.I. Furthermore, the P.I. has staff trained and dedicated to performing these studies. All catheters will be inserted with meticulous use of sterile technique to avoid infection and great care will be taken to minimize any discomfort or complications associated with insertion. The catheters will be kept patent with heparinized saline to prevent clotting.

- **CCT, OGTT and HCG-ST** – The major risk associated with these tests is insertion of an intravenous catheter for blood drawing as discussed above. Glucose ingestion during the OGTT may cause abdominal discomfort, nausea, increased blood pressure, flushing or sweating. Dairy cream ingestion may cause urticaria, pruritus and in rare cases anaphylaxis in individuals with an unknown dairy allergy; and much less often may cause nausea, cramps, flatulence, bloating or diarrhea in individuals with previously unknown lactose intolerance.
- **FS-IVGTT** – The major risk of this test is hypoglycemia associated with the insulin infusion along with the risk associated with insertion of intravenous catheters for the infusions and blood drawing as discussed above. The frequent glucose measurements will allow prompt detection of hypoglycemia, in which case the test will be stopped and the intravenous glucose infusion will be increased or glucose will be given orally for resolution.
- **DEXA scans** involve a very small amount of radiation. One of the risks associated with radiation exposure is cancer. The natural incidence of fatal cancer in the U.S. is about 1 chance in 5. Everyday radiation exposure from natural occurring background radiation (sun, radon exposure in the home) is approximately 100 mrem (1 mSv) per year. Each subject in this study will receive a whole body DEXA scan. The radiation dose of one whole body DEXA scan is approximately ≤ 0.3 mrem. This amount of radiation is very low as to make an accurate risk estimate meaningless. A negative urine pregnancy test must be documented prior to undergoing the DEXA scan.
- **HCG Administration** – HCG use can cause the following adverse effects: edema, depression, fatigue, headache, irritability, restlessness, ovarian cyst rupture, reaction or pain at the injection site, or a local or systemic hypersensitivity reaction.

The risk of cyst rupture will be minimized by administering the HCG between days 3 and 13 following the onset of either a spontaneous or progestin-induced withdrawal bleed, or without regard to the onset of menses if vaginal sonography within 21 days of HCG administration reveals no evidence of follicle cyst development in the face of a negative pregnancy test.

- **Salsalate Treatment** – Salsalate use can cause the following adverse effects characteristic of salicylates in descending order of frequency: tinnitus, nausea, hearing impairment, rash and vertigo. These effects are transient, and resolve upon cessation of salsalate. Although cause and effect has not been established, the following less common adverse effects have also been reported: abdominal pain, abnormal hepatic function, anaphylactic shock, angioedema, bronchospasm, decreased creatinine clearance, diarrhea, gastrointestinal irritation, inflammation, bleeding or perforation, hepatitis, hypotension, nephritis, urticaria, myocardial infarction or cerebral vascular accident.

Tinnitus is an expected side effect of salsalate treatment that occurs more frequently at doses higher than the one proposed for this study. To minimize this side effect, subjects will be advised to begin by taking one capsule (i.e. 500 mg of salsalate in subjects receiving salsalate) the first day and increase the dose in one capsule increments every 3 days thereafter until the desired dose is achieved. If tinnitus occurs at any point in the upward dose titration or later on during the treatment, an affected subject will be advised to reduce the daily study medication dose in stepped one capsule increments every 3 days. In a previous study, this approach effectively resolved symptoms enabling subjects to complete the study while still maintaining therapeutic salicylate levels. The nature of any suspicious symptoms reported by a subject will be reviewed to determine whether there is actual tinnitus before the salsalate dose is reduced in the manner described. Vital signs and potential side effects will be monitored every 4 weeks during treatment when subjects report to the CRC to have their blood draw for a salicylate level. Liver function tests, BUN and creatinine levels will be drawn within 4 weeks after study completion to be certain that no lasting untoward hepatic or renal impairment has occurred.

- **Reproductive Risk** – Pregnancy is an exclusion criterion for this study. The risks listed above would apply equally to a developing fetus as well as the primary participant. Potential risks of specific impact to a developing fetus include the small amount of radiation exposure received from the DEXA scan (point 4 above). A negative urine pregnancy test must be documented prior to undergoing the DEXA scan. Salsalate is a Category C drug for pregnancy and use of double barrier contraception will be required during the study unless either the participant or her partner have already undergone permanent sterilization.
- **Loss of confidentiality** is a risk as with all human subject-based medical research owing to disclosure of health information. These disclosures may be mandated by local or national regulatory agencies (i.e. IRB, Food and Drug Administration (FDA)) or may be unintentional. Safeguards regarding both physical and electronic copies of all subject data are in place, as dictated by the current standards of UIC and UI Health.

Except for de-identified research data, all other information relevant to patients collected in the study will be kept confidential, including locked storage of all paperwork, and secure digital storage on a database to which only members of the research group have access. The security and integrity of this database are maintained with the direct assistance and oversight of UI Health Information Technology support teams, and the database is served centrally from a closely monitored, regularly backed up server.

- **Unforeseen Risks** – There may be risks or side effects related to the study that are unknown at this time.

Benefits

- Subjects will receive individual body composition results as well as diabetes risk information from the OGTT. Based on the results of a small pilot study that treated women with PCOS with salsalate, it is possible that subjects receiving salsalate may experience a reduction in circulating androgens and ovulation. However, because individuals respond differently to therapy, it is not known in advance if these potential benefits will occur. There are no anticipated benefits to subjects receiving placebo.

The knowledge to be gained from this research may be beneficial to other patients, society or science. The results will guide the design of future studies aimed at determining what dietary modifications, medical regimen or both will optimally attenuate inflammation in PCOS with the goal of reducing medical disease and enhancing fertility. In particular, the findings may help define the therapeutic molecular inflammation target to develop the most ideal anti-inflammatory agent.

